#### G. ALERT ASSESSMENT FRAMEWORK

This project is intended to be a methods evaluation rather than a regulatory safety analysis of these two anti-seizure medications. For each of the analytic datasets (i.e., scenarios) considered, alerts will be

defined according to the criteria described above per method. Generally, we proposed to use the method as it has been used in practice with slight modifications.

At the most basic level, alerts will be triaged as known or expected based on the study exposure's label, known safety profile or temporal administration pattern. We will also record nodes that alert in any given method across several analytic scenarios (e.g., alerts that are robust to the choice of comparison windows).

For the empiric assessment, we will record the total alert load, the alignment with the known or expected alerts, and the influence of the various study design choices examined. For the simulation assessment, we will record the ability to detect pre-specified, investigator-inserted risks.

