#### A. EMPIRICAL COMPARISONS:

We have identified two study exposures of interest and will evaluate these two exposures with all three methods. We will not name a primary analysis as this is a methods evaluation that will involve multiple comparisons varying a) the grouping of outcomes of interest, b) the timing of the referent comparison windows relative to exposure, and c) the length of such windows. A full list of analyses is listed later in this protocol in **Table 1**. The empiric evaluation provides a real-world assessment of the performance of each method when applied to drugs with well-characterized safety profiles.

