## III. METHODS

#### A. SURVEILLANCE POPULATION, ENROLLMENT CRITERIA AND STUDY EXPOSURES

Data will be obtained from Optum ClinInformatics from the years 2004 to 2016. We will include individuals who were dispensed the study exposures of interest on or after their 18th birthday during the available date range without further inclusion or exclusion criteria.

There are two study exposures of interest: oral forms of levetiracetam and lamotrigine used in the adult population. Additionally, there is one "calibration" exposure that must be collected to implement one of the methods. The two study exposures were chosen because they have relatively well-characterized safety profiles and are used primarily for treatment for seizure disorders which are medical conditions that are not usually associated with rapid changes in overall clinical status (except for rate of seizures itself). Stability in the expected underlying clinical status is especially important when implementing self-controlled designs to isolate the effect of the exposure itself rather than other temporal confounding factors (e.g., generally declining or improving health state), a concept described in epidemiology as exchangeability. Self-controlled designs compare time periods and it is only a fair comparison when factors outside of the incident dispensing of the study exposure are held as equal as possible through either design or analysis techniques. When the general risk of the health outcomes of interest is equivalent but for the study exposure, then the differences between the observed and expected rate beyond a predefined statistical threshold signifies a potential causal hypothesis requiring further investigation.

Although we will not assess outcomes in the period of time immediately preceding the incident dispensing of the study drug of interest, we still expect that both of these anti-seizure medications may show an increased frequency of seizure-related disorders in the pre-exposure comparison window. Nonetheless, we have chosen to include these outcomes within the groupings of outcomes being assessed. Lamotrigine also has other on- and off-label uses for mood disorders or pain that may create additional time-varying confounding by indication. We expect to triage any increased frequency of these adverse outcomes with these acknowledged limitations.

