#### 4. Concomitant condition evaluated at the medical visit

We will exclude Day 0 in the analysis to prevent capturing conditions that were present at the time of exposure. However, it is still possible that an individual has evidence of an incident exposure that cooccurs with evaluation of unrelated symptoms or medical conditions. Follow-up evaluation or treatment for the unrelated condition may then appear to be associated with the study drug.

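### Empirical alignment is measured against one merged class of known or expected alerts, so it cannot separate recovered labelled reactions from timing-explained alerts or count labelled reactions missed

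*Protocol*

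**What the plan says.** Section III.G of the protocol describes the classification: "alerts will be triaged as known or expected based on" any of three grounds. These form a single class and are given, for each study drug, as its "label, known safety profile or temporal administration pattern". For the empirical arm it then states that "we will record the total alert load, the alignment with the known or expected alerts" and the influence of the design choices. For the simulation it records detection of the inserted risks.

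Section II.A explains what the empirical arm is for: "The empiric evaluation provides a real-world assessment of the performance of each method when applied to drugs with well-characterized safety profiles". Section III.A gives the well-characterized profiles as one reason for choosing levetiracetam and lamotrigine.

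Two other sections describe alerts or excesses that are not drug reactions. On lamotrigine's mood and pain uses, section III.A foresees "additional time-varying confounding by indication. We expect to triage any increased frequency of these adverse outcomes with these acknowledged limitations". Section III.H.4, on conditions evaluated around the dispensing visit, warns: "Follow-up evaluation or treatment for the unrelated condition may then appear to be associated with the study drug".

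**The concern.** Drugs with known safety profiles are useful for testing a detection method because the answers are partly known in advance. That benefit requires two things: labelled reactions must be distinguishable from everything else, and those that do not alert must be counted.

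The wording in III.G secures neither. The three grounds are joined by 'or' into one class, so a recovered labelled reaction and an alert explained by visit timing enter the same tally. The thing classified is an alert, so a labelled node that stays silent has no place among the listed results.

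This matters for the comparison of methods. Section III.F.2 says that the conditional Bernoulli statistic and the ICTPD calibration share the intention of controlling for global patterns of healthcare use. A method that succeeds in suppressing timing artefacts gets no recognition from alignment, while the artefacts another method raises may be filed as expected.

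**Working it through.** The plan gives no figure to reproduce: it states no number of labelled reactions and no alignment formula. All counts in steps 1 to 3 are assumed and serve only to show what the recorded quantities can distinguish.

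**Step 1. Alignment read as a share of alerts.** Let L be labelled alerts, T timing-explained alerts and U unexplained alerts. Then alignment = (L + T)/(L + T + U), and the labelled share = L/(L + T + U).

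| | L | T | U | Alignment | Labelled share |
|---|---|---|---|---|---|
| Method 1 | 8 | 0 | 2 | 8/10 = 0.80 | 8/10 = 0.80 |
| Method 2 | 2 | 6 | 2 | 8/10 = 0.80 | 2/10 = 0.20 |

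Alert load (10 each) and alignment (0.80 each) are identical, yet one method recovered four times as many labelled reactions.

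**Step 2. Alignment read as overlap with an expected set.** Suppose the set holds R labelled and S timing-related nodes. Method 1 hits 8/(R + S) and method 2 hits (2 + 6)/(R + S) = 8/(R + S). They tie for any R and S. The merging problem does not depend on which reading is meant.

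**Step 3. Missed labelled reactions.** Sensitivity = L/R needs R, which the protocol does not fix.

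| R | Method 1 (L = 8) | Method 2 (L = 2) |
|---|---|---|
| 10 | 0.80 | 0.20 |
| 20 | 0.40 | 0.10 |
| 40 | 0.20 | 0.05 |
| 80 | 0.10 | 0.025 |

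The same 8 labelled alerts are compatible with sensitivity anywhere from 0.10 to 0.80 over this range.

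**Step 4. Which confounding can raise an alert.** Equation 1a has an indicator that sets the LLR to zero unless the risk-window share exceeds p. The risk window and each comparison window last 28 days, so p = 28/56 = 0.5. With assumed counts:

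- 40 risk, 80 comparison: share 40/120 = 0.33 < 0.5, so LLR = 0 and there is no alert.
- 80 risk, 40 comparison: LLR = 80 ln(0.667/0.5) + 40 ln(0.333/0.5) = 23.01 − 16.22 = 6.80.

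Indication-related events that cluster before dispensing therefore suppress TreeScan alerts for the two pre-exposure windows in Table 1. ICTPD, which alerts only when its lower credible limit is positive, behaves the same way in direction. Timing-explained alerts would come mainly from the [36,63] comparison or from follow-up care after Day 0.

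**Step 5. Does the simulation cover the gap?** Section II.B randomizes all outcomes without an inserted association at their background rates. As described, it does not reproduce real indication or follow-up patterns, so behaviour under such patterns can be seen only in the empirical arm.

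**The case against.** The strongest case against the point has five parts.

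- **No score is defined.** The protocol records alignment without a formula, names no primary analysis (II.A) and aims to describe variation between methods (I). A reader might infer that a sparse or confounded method would be ranked first. For example, with 20 assumed labelled nodes, a method with 10 labelled and 5 unexplained alerts has alignment 10/15 = 67% and sensitivity 10/20 = 50%; one with 2 labelled and 4 timing alerts has 6/6 = 100% and 2/20 = 10%. That reversal needs both an assumed formula and assumed counts. The loads, 15 against 6, would also be reported beside it. This part stands.
- **Detection of known effects belongs to the simulation**, where the denominator is known, and no empirical sensitivity is promised. This stands as a limit on scope, but II.A still calls the empirical arm an assessment of performance.
- **Post hoc classification is not stated.** A reader might infer it from the wording about triaging alerts. The protocol does not say so, section III.A sets out some expectations beforehand, and an SAP that is not shown could hold a list. This stands. A list built on the merged class would still merge the two kinds of alert.
- **Temporal administration pattern is undefined**, and calling an alert expected does not credit it as a true reaction. Sections III.A and III.H.4 support reading the term as timing-related confounding, but that remains an inference.
- **Misses can be seen by comparing methods** run on the same dataset. This is partly so: a labelled node missed by every method stays invisible.

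**Conclusion.** The point holds for the empirical arm. As worded, III.G pools labelled reactions with timing-explained alerts and applies the pool to alerts without a stated reference set. The quantities it lists can neither separate the two kinds of alert nor show how many labelled reactions each method missed. The first conclusion follows from the wording under either reading of alignment; the second rests on no reference set being stated in the protocol. Treating the timing ground as confounding relies on sections III.A and III.H.4.

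The size is unknown, because the documents give no counts. The documents do not support saying that the ranking of methods is reversed, that confounded alerts are formally credited, or that the triage is post hoc. Nor is the study's measurement of power for inserted risks affected. This is a worthwhile and cheap improvement, not a flaw that invalidates the study.

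**What to change.** Before running any method, fix two lists for each study drug:

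1. Labelled reactions mapped to MLCCS nodes, with stated rules for plausibility within days 1-28 and for the minimum node count needed for inclusion.
2. Nodes related to the indication or to visit timing.

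In III.G, replace the single class with three groups reported separately for each method and analytic dataset: labelled, explained by indication or timing, and other. Add the proportion of listed labelled nodes that alerted. Describe the remaining alerts as unexplained rather than false, since an unlabelled alert is not proof of error.

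The cost is a one-off mapping exercise, much of which the planned triage would need anyway, plus a short results table. No dataset or detection method changes. The drawback is that some label terms map imperfectly to MLCCS nodes, and the inclusion rules require judgement that should be written down beforehand.

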#### B. SIMULATED DATA ASSESSMENTS:

Using empirical data gathered for the two study exposures of interest, we will choose some outcomes and add investigator-inserted occurrence during the risk window according to a pre-specified simulated association. The occurrence of all other outcomes will be randomized according to their background rate occurrence. The resultant simulated dataset will then consist of "positive" outcomes with pre-specified

associations and the rest will be "null outcomes." We will vary the strength of the simulated association and the prevalence of the outcomes with the simulated association to evaluate the statistical power of the three methods to detect the investigator-inserted elevated frequency. The simulation is important because it evaluates each method's statistical power in detecting known associations that have been artificially inserted at different elevated risk levels.

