#### 1. TreeScan:

We will use both the conditional and unconditional Bernoulli tree-based scan statistic that detects elevated frequencies of outcomes in pre-specified time periods. We do not plan on testing the tree-temporal scan statistic although the data collected could be repurposed in a separate project. TreeScan™ (www.treescan.org) is a data mining method that scans electronic health data that are organized into clinically relevant groupings of medical product exposures or health outcomes. With respect to the self-controlled risk interval design, TreeScan has been evaluated in simulation environments. as well as empirical environments. For a pre-defined exposure, it adjusts for the multiple testing inherent in evaluating thousands of potential adverse events to assist with prioritization of alerts or statistically significant findings for further investigation.

Two versions of the Bernoulli test statistic are planned for this evaluation, and both rely on the computation of the log likelihood ratio for each outcome node *LLR(G)*. The test statistic *T* is the maximum log likelihood ratio across all observed nodes. For hypothesis testing using *T*, the p-value is derived non-parametrically using Monte Carlo simulation. Under the null hypothesis, there is no association between the study exposure and any outcomes. If the null hypothesis is true, each event within a node is expected to occur in relationship to the length of the risk and comparison windows. The conditional version of the test statistic adjusts this probability by accounting for the overall pattern of outcomes in both windows (see equations below). In both versions, when performing Monte Carlo simulations, all nodes must contain the same total number of outcomes per node as observed in the original data. They are assigned to occur across the observation window per the null hypothesis to derive the test statistic used to generate an alert (i.e., a statistically significant departure from the null hypothesis).

- 8 -

Equation 1a (Unconditional): LLR = 
$$\ln\left(\frac{\left(\frac{c_G}{c_G + n_G}\right)^{c_G} \left(\frac{n_G}{c_G + n_G}\right)^{n_G}}{(p)^{c_G}(1-p)^{n_G}}\right) I\left(\frac{c_G}{c_G + n_G} > p\right)$$

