$$Equation \ 1b \ (Conditional): LLR = \ln\left(\frac{\left(\frac{C_G}{C_G + n_G}\right)^{c_G} \left(\frac{n_G}{C_G + n_G}\right)^{n_G}}{\left(\frac{C}{C + N}\right)^{c_G} \left(\frac{N}{C + N}\right)^{n_G}}\right) I\left(\frac{c_G}{c_G + n_G} > \frac{C}{C + N}\right)$$

Equation 2:  $T = {}^{\max}_{G} LLR(G)$ 

Where: T = Bernoulli tree scan statistic

- G = node of interest
- $c_{\mathsf{G}}$  = number of outcomes in the risk window for a given node  $\mathsf{G}$
- $n_{G}$  = number of outcomes in the comparison window for a given node G
- p = ratio of the risk window length to the entire observation window length
- C = total number of outcomes in the risk window across ALL nodes
- N = total number of outcomes in the comparison window across ALL nodes

*I()* is the indication function, which is 1 when there are more outcomes in the risk window than would be expected by chance. It is included to ensure that we are looking for an excess risk of the having the adverse event rather than a protective decreased risk.

We will use an alerting threshold of p=0.01. In other words, we will evaluate nodes with log-likelihood ratios that fall into the top 1% of the maximal log-likelihood ratios observed using Monte Carlo. These nodes represent the most extreme departures from the null hypothesis.

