#### 2. Information Component Temporal Pattern Discovery:

Information Component Temporal Pattern Discovery (ICTPD) is another longitudinal signal detection method that can be applied to self-controlled designs. ICTPD uses a shrinkage estimator to reduce the number of false positives due to random variability (and then indirectly the multiple comparisons) or due to very low expected values for rare adverse events or exposures. It does not explicitly control for multiplicity. The information component with shrinkage  $IC_{\Delta}$  can be calculated as shown below. The more general formula allows for accounting of censoring between the risk window and control window, but this study will require overall enrollment in both. There is a closed form solution for the credibility interval of the  $IC_{\Delta}$ .

$$IC_{\Delta} = \log_2 \left( \frac{y_1 + \frac{1}{2}}{y_0 \left( \frac{E_1}{E_0} \right) + \frac{1}{2}} \right)$$

Where:  $y_1$  = number of outcomes in the risk window among study exposure of interest

 $y_0$  = number of outcomes in the comparison window among study exposure of interest

 $E_1$  = number of outcomes in the risk window among the external calibration exposure of interest

 $E_{0}$  = number of outcomes in the comparison window among the external calibration exposure of interest  $% \left( {{E_{0}}} \right) = {E_{0}} \right)$ 

ICTPD makes use of an external calibration mechanism to control for global patterns of healthcare utilization that may account for systematic differences between pre- and post- exposure windows. It has a similar intention to the conditional Bernoulli version of the tree scan statistic described above but is implemented differently. The conditional Bernoulli version of the tree-based scan statistic utilizes the pattern of outcome occurrence in the entire MLCCS tree to control for global patterns of healthcare. The ICTPD uses an external exposure group – specifically, all exposures using all dispensing or prescription

records – and then performs the adjustment in a node-specific fashion. Using node-specific notation similar to the equations above, the  $IC_{\Delta}$  can be re-written below:

$$IC_{\Delta} = \log_2\left(\frac{c_G + \frac{1}{2}}{n_G\left(\frac{C_G}{N_G}\right) + \frac{1}{2}}\right)$$

where: G = node of interest

 $c_{\rm G}$  = number of cases in the risk window for a given node G among the study exposure of interest

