 $n_{G}$  = number of cases in the comparison window for a given node G among the study exposure of interest

 $C_{G}$  = total number of cases in the risk window for a given node G among the calibration exposure population

 $N_G$  = total number of cases in the comparison window for a given node G among the calibration exposure population

In our study, access to all dispensing records (i.e., a "general" population) is not feasible so we will randomly select 100 NDC and HCPCS codes and combine their data to create our "calibration exposure."

The traditional alerting threshold for the ICTPD method uses a 2-sided 95% credible interval, denoted  $IC_{\Delta 025}$ . An alert occurs only when this value is positive, implying that an alert is only raised for an unusual elevation in the frequency of observed outcomes in the risk window. The indication function in the test statistic for TreeScan performs the same function. For this analysis, we will observe the number of alerts when  $IC_{\Delta 025} > 0$  and when  $IC_{\Delta 01} > 0$ .

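### The simulation compares the methods' power at very different, unrecorded false-alert rates, so method and alert threshold are confounded

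*Protocol*

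**What the plan says.** Section II.B gives the purpose of the simulation: to "evaluate the statistical power of the three methods to detect the investigator-inserted elevated frequency". Each simulated dataset holds outcomes with an inserted association, and all remaining outcomes are null by construction.

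The alert rules are in section III.F:

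- **TreeScan (III.F.1).** "We will use an alerting threshold of p=0.01". The protocol explains this as nodes with "log-likelihood ratios that fall into the top 1% of the maximal log-likelihood ratios observed using Monte Carlo", and says of the method that "it adjusts for the multiple testing inherent in evaluating thousands of potential adverse events".
- **ICTPD (III.F.2).** "The traditional alerting threshold for the ICTPD method uses a 2-sided 95% credible interval", with an alert when the lower limit is positive. The protocol adds a second version at the 1% limit. Of multiplicity it says: "It does not explicitly control for multiplicity". Shrinkage is offered as an indirect protection.
- **SSA (III.F.3).** It has no threshold and no multiplicity control. The number of SSA alerts is set to the larger of the TreeScan and ICTPD counts, taking the largest absolute differences.

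Section III.G lists the measures. For the empirical data these are total alert load, agreement with known or expected alerts, and the influence of design choices. For the simulation it gives one: "For the simulation assessment, we will record the ability to detect pre-specified, investigator-inserted risks".

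**The concern.** Power has meaning only beside the false-alert rate at which it was obtained. The protocol fixes one familywise rule, one per-node rule and one borrowed count, and then names detection as the only simulation measure. The ICTPD version at the 1% limit invites a misreading, because it looks matched to TreeScan's 0.01 although one level applies to each node and the other to the whole tree.

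The simulation is also the only part of the study in which the null outcomes are known to be null. Alert load in the empirical data cannot take its place. If false alerts are not recorded in the simulation, a method without multiplicity control can show high detection while the price paid for it stays out of view.

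**Working it through.** The protocol gives no power or false-alert figure, so there is none to reproduce. The check asks how far the threshold alone can move power when the statistic is held fixed.

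**Inputs from the protocol**
- Risk window of days 1-28 (section III.E) and 28-day comparison windows (Table 1), so p = 28/(28 + 28) = 0.5 in Equation 1a.
- TreeScan: 0.01 on the maximum log-likelihood ratio (LLR). ICTPD: nominal one-sided 0.025 or 0.01 per node.

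**Assumptions, because the protocol gives no values**
- M = 1,000 to 5,000 nodes (the protocol speaks of thousands), independent and not nested, with skewed totals (median 20 events).
- Poisson counts. Risk ratios (RR) of 1.5 to 3 with 20 to 100 expected comparison-window events.
- Nominal ICTPD levels, because the closed form of its interval is cited but not shown.

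**Step 1: put the levels on one scale.** A familywise level of 0.01 over M independent nodes needs a per-node level of 1 − 0.99^(1/M). This is 1.0 × 10⁻⁵ for M = 1,000 and 2.0 × 10⁻⁶ for M = 5,000. The ICTPD levels are therefore about 1,000 times (0.01 / 1.0 × 10⁻⁵) to 12,500 times (0.025 / 2.0 × 10⁻⁶) looser.

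**Step 2: expected false alerts if every node is null (M × α).**
- At 0.01 per node: 1,000 × 0.01 = 10 and 5,000 × 0.01 = 50.
- At 0.025 per node: 1,000 × 0.025 = 25 and 5,000 × 0.025 = 125.
- The chance of at least one false alert, 1 − (1 − α)^M, exceeds 0.9999 in every case.
- Exact binomial tests on these small counts are conservative and give fewer: about 5 to 24 at 0.01 and 13 to 65 at 0.025.
- TreeScan rule, simulated: critical LLR 9.01 (M = 1,000) and 10.45 (M = 5,000). The chance of any false alert was 0.014 and 0.011, with mean counts 0.014 and 0.011. This is consistent with 0.01 given Monte Carlo error in the critical value.

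**Step 3: power of the same LLR at three cut-offs.** The nominal one-sided levels 0.01 and 0.025 correspond to LLR cut-offs of 2.71 and 1.92. Entries are for M = 1,000, with M = 5,000 in brackets.

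| RR, comparison events | Familywise 0.01 | 0.01 per node | 0.025 per node |
|---|---|---|---|
| 2, 20 | 4% (2%) | 61% (62%) | 74% (75%) |
| 1.5, 100 | 14% (8%) | 80% (81%) | 89% (89%) |
| 2, 50 | 45% (33%) | 96% (96%) | 99% (98%) |
| 3, 50 | 99.9% (99.7%) | 100% (100%) | 100% (100%) |

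The per-node cut-offs do not depend on M, so differences within those two columns are simulation noise.

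**Step 4: check by hand.** At RR 2 with 50 comparison events the expected counts are 100 and 50. The LLR there is 100 ln(4/3) + 50 ln(2/3) = 28.77 − 20.27 = 8.50. That lies just below 9.01, further below 10.45 and far above 2.71, as the third row shows. At RR 3 with 50 events the counts are 150 and 50, and the LLR is 150 ln(1.5) + 50 ln(0.5) = 60.82 − 34.66 = 26.16. That clears every cut-off, so the gap closes.

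**Step 5: SSA.** Its alert count equals the larger of the other two. Where ICTPD gives tens of alerts, SSA does as well, whatever the SSA statistic shows.

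**The case against.** The strongest reply is that the thresholds are a disclosed choice. Section III.G says each method is to be used broadly as in practice, and sections III.F.2 and III.F.3 state openly that ICTPD and SSA lack multiplicity control. The stated aim is to describe variation in findings, and no passage promises a ranking. This stands as a defence of the conventional thresholds, which should remain in the report. It does not defend reporting detection without false alerts, since a comparison of methods as practised needs both.

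A second reply is that false-positive summaries are often left to an analysis plan, and section III.G does not say that detection is the only measure. That is fair as far as it goes. But the protocol itself fixes the three alert rules and chooses the simulation measure, and it assigns alert load to the empirical part alone.

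A third reply concerns SSA. It is matched on alert load to the looser comparator, so that pair is more comparable than TreeScan and ICTPD. This is correct, but equal alert load is not an error rate.

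Two stronger readings are tempting and are not supported:

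- A reader might infer that the results will show the thresholds instead of the methods. Multiplicity adjustment belongs to TreeScan, and shrinkage and node-specific calibration belong to ICTPD. They contribute too; as planned, their effect and the threshold's cannot be separated.
- A reader might infer that the ICTPD rule is looser than its nominal per-node level because its expected count is itself estimated. The protocol does not give the interval formula, so the actual per-node rate cannot be derived from it.

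**Conclusion.** The point holds as a confounding of method with threshold. The planned detection results would come from alert rules that differ by tens of expected false alerts per dataset, and the plan names no record of those alerts. With the statistic held fixed, the threshold alone moves power from 33-45% to 96% or more at RR 2 with 50 comparison events. It makes almost no difference for strong, common effects.

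The sizes rest on assumed node counts, event counts, risk ratios and independent nodes, and on nominal ICTPD levels. Nesting in the real tree would change the familywise figures and the clustering of alerts, but not the expected count M × α. The table compares thresholds on one statistic and does not predict the power of ICTPD or SSA. The power the methods would show at a matched false-alert rate cannot be computed from the protocol.

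**What to change.** In section III.G, for every simulated dataset and method, also record:

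- the number of null outcomes that alert;
- whether any null outcome alerts;
- the proportion of alerts that are false.

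State which nodes count as null, since a parent node that contains an inserted-risk outcome is not null. Report power beside these figures at the thresholds used in practice.

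Add a comparison at a matched false-alert level, for example power plotted against the number of null alerts, with nodes ranked by a node-standardised measure such as a per-node tail probability.

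Do not match by a cut-off on the maximum raw ICTPD lower limit or on the raw SSA absolute difference. Sparse nodes dominate the first and common nodes the second. In a trial run with an assumed gamma interval on 4,000 sparse nodes holding 20,000 outcomes, the 99th percentile of the maximum ICTPD lower limit was about 3.5 to 3.7 on the log2 scale. A true RR of 3 is only log2(3) = 1.58, so ICTPD would then detect nothing even at RR 3 with 100 events.

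The cost is protocol wording and extra summaries of simulations already planned. Some all-null replicates may be needed, which the protocol does not now describe. No new patient data are required.
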